8.7 Week 16 (post-randomisation) and every 6 weeks until progression

- Toxicity assessment
- Physical examination including vital signs, Blood pressure, weight
- Concomitant drug history
- ECOG performance status
- Full blood count and clotting (PT, INR) and serum biochemistry
- Alpha feto-protein
- Documentation of Child-Pugh score
- ECG
- QoL assessment
- Review and collect patient diary
- Radiological assessment of response as per standard of care.
 - If progressive disease is identified at radiological review, ensure the Trials Unit are informed immediately using the Progression Notification Form (see section 3.2).

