11 QUALITY OF LIFE

QoL is an important outcome measure and as such all patients will be invited to participate in the QoL study. Patients who consent will be assessed using validated instruments developed by the EORTC QoL Group: the EORTC QoL questionnaire (QLQ-C30) version 3 and EORTC QLQ-HCC18 a site-specific module for HCC. The EORTC questionnaires will assess both general and hepatocellular specific aspects of quality of life. Patients will also be asked to complete a EuroQoL (EQ-5D) questionnaire which will enable the patient's current health state to be valued for use in calculating quality-adjusted life years (QALYs). These will be collated into a QoL booklet which will be given to patients to complete prior to treatment with the reasons for any non-compliance recorded. QoL booklets will be coordinated with routine clinic visits and requested at baseline, pre TACE, week 10 and 6-weekly thereafter until progression.

The EORTC QLQ-HCC18 site-specific module for HCC has completed phases 1 to 3 of questionnaire development, and has been approved by the EORTC module development committee and currently submitted for publication.

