13.2 Analyses of Outcome Measures

All analyses will be carried out on an intention to treat basis, retaining patients in their randomised treatment groups and including protocol violator and ineligible patients, in order to maintain the unbiased comparison of treatments created by the randomisation procedure. A sensitivity analysis excluding ineligible patients may be conducted and reported. Analyses will be according to the detailed Statistical Analysis Plan (SAP) for the Trial using the statistical software packages Stata, SAS and R. The SAP is version controlled and any amendments to the plan will be documented.

The primary aim is to test the null hypothesis of no difference between the two treatment arms in terms of PFS. Disease status is assessed under the RECIST criteria. The primary analysis will consider the local disease assessment only. A sensitivity analysis based on the results of the central review of disease status may be performed. Survival estimates (progression-free, overall and time to progression) will be calculated using the method of Kaplan and Meier, and the Mantel-Haenszel version of the log-rank test will be used to assess differences in survival estimates across treatment groups and across important patient characteristic or histological groups. Any treatment effect will be adjusted by

stratification factors and other identified prognostic factors using stratified log-rank analyses and in a multivariate setting using Cox proportional hazards and/or random effects modelling. Hazard ratios of the treatment effect (without significance testing) within identified prognostic subgroups will be estimated and presented graphically with tests of heterogeneity. Analyses of overall survival may be confounded since patients can crossover to the active arm upon disease progression. These analyses are sensitive to the assumption of proportional hazards and, as such, methods that adjust for this confounding will be considered once the assumption can be assessed.

Toxicity will be graded according to the NCI CTCAE v4 criteria and the proportions of grade 3/4 toxicity will be reported descriptively across treatments. Additional treatment required during or after protocol treatment will be recorded and presented descriptively across treatment groups.

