Objective Disease Response will be determined according to the RECIST criteria and patients will be grouped for comparison across treatments according to their 'best' response. Response rates are calculated by dividing the total number of patients with CR or PR (on 'best' response) by the total number of patients randomised per treatment group. The proportions of patients achieving a response will be compared descriptively with 95% CI and compared across treatments using Pearson's chi-square test.

Quality of life will be analysed using longitudinal statistical methods comparing treatment group with appropriate consideration given to missing data due to dropout and death. Questionnaire responses will be combined and transformed into dimension scores and the mean change from baseline score compared using the Mann-Whitney test. Standardised area under the curve analysis will be used to assess mean observed symptomatic and functional QoL over a complete period of 12 months from randomisation whilst minimising multiple testing. Global QoL scores and utility scores form the EQ-5D will be assessed in a quality-adjusted survival analysis to enable simultaneous assessment of QoL and survival, to account for drop-out due to death and censored QoL estimates (from patients remaining alive). Quality adjusted survival analysis within 12 months of randomisation using the integrated quality-survival product method will be used.

The number of additional TACE procedures will be recorded in each arm and reported descriptively with medians and ranges.

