APPENDIX 12: FLOWCHART OF ASSESSMENTS

	Screening (within 28 days prior to rand.)	Day 1 (day of randomisation)	Up to 72 hours Pre-TACE	TACE Day 0	TACE Day +1	TACE Day+7	Week 10 (post randomisation)	Week 16 (post randomisation)	Week 22 (post randomisation)	Every 6 WEEKS thereafter (until week 22 then as per standard of care thereafter)
Informed consent	х									
Confirmation of diagnosis of HCC according to AASLD guidelines or histology	х									
Medical history includes prior surgery, prior chemo/radiation, allergy, cardiac history	х									
Toxicity assessment			x			х	Х	х	X	х
Physical examination including vital signs, height, weight and physical exam of organ systems	х	х	х				х	х	х	х
Blood pressure	x	х	x			х	х	х	х	х
ECOG performance status	х	х	x			х	Х	х	X	х
Concomitant drug history	х	х	x				Х	х	X	х
Full blood count and clotting (PT, INR) and Serum biochemistry ¹	х	х	x			х	х	х	х	х
Alpha fetoprotein	х	х	x				Х	х	X	Х
Hepatitis B and C antigen and antibody	х									
Amylase	x									
ECG	x		x			х	х	х	х	Х
LVEF determined by either MUGA scan or echocardiogram	x									
Chest CT and dual phase CT or contrast enhanced MRI scan of abdomen ²	x						х		х	
Documentation of Child-Pugh score	x	х	x			х	х	х	х	х
QoL assessment		x ³	х				x	х	х	Х
Pregnancy test in women of child bearing potential	x									
Collection of Biomarker blood	x	х	х		х		х		х	
Arrangements for TACE to be performed within 2-5 weeks from randomisation		х								
Commence study drug - sorafenib or placebo		х								
TACE				х						

¹ Biochemistry to include Urea, Cr, Na, K, Ca, Alb, Bili, Aphos, ALT (or AST), GGT
2 CT scans to be performed at every 12 weeks (coincides with visits at weeks 10, 22, etc) until week 22 and as per local standard of care thereafter. To ensure comparability, the baseline X-rays/CT scans and subsequent X-rays/CT scans must be performed using identical tech scans performed immediately following bolus contrast administration using a standard volume of contrast, the identical contrast agent, and preferably the same scanner). Each lesion must be followed with the same method throughout the study (from baseline until progression). 3 QoL questionnaire should be administered before randomisation or at randomisation, before the patient is informed of the treatment to which he is assigned.

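### Quality-of-life booklets stop at progression, but section 13.2 plans an area-under-the-curve and a quality-adjusted survival analysis over 12 months from randomisation

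*Protocol*

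**What the plan says.** **Collection.** Section 11 has the QoL booklets (EORTC QLQ-C30, QLQ-HCC18 and EQ-5D) "requested at baseline, pre TACE, week 10 and 6-weekly thereafter until progression". Section 12.6 repeats this schedule. The visit list that carries the QoL assessment, section 8.7, is headed "Week 16 (post-randomisation) and every 6 weeks until progression". Section 3.2 keeps patients in follow-up after progression, and the form table in section 14.1 lists a post-progression follow-up form. Neither mentions QoL.

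**Flowchart.** In Appendix 12 the last column, which also carries a QoL mark, is headed "Every 6 WEEKS thereafter (until week 22 then as per standard of care thereafter". That does not agree with six-weekly visits until progression.

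**Analysis.** Section 13.2 plans a standardised AUC of mean observed QoL "over a complete period of 12 months from randomisation". It adds: "Quality adjusted survival analysis within 12 months of randomisation using the integrated quality-survival product method will be used". On missing data it promises "appropriate consideration given to missing data due to dropout and death", and it also refers to censored QoL in patients who are still alive. The section opens with "All analyses will be carried out on an intention to treat basis".

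**The concern.** The data window closes at progression, while the analysis window closes at month 12. Between progression and the earlier of death and month 12, no QoL is planned for any patient. This is a gap built into the design. It is also informative, because the event that ends collection is part of the primary endpoint.

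If sorafenib delays progression as the sample size assumes, collection ends earlier on placebo. The two planned analyses are affected differently:

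- The AUC becomes an average of pre-progression QoL over windows whose length depends on outcome and arm.
- The integrated quality-survival product multiplies survival by the QoL of survivors. After progression the only QoL available comes from patients who are still progression-free, so survival time after progression is weighted by the health of a different, selected group.

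QoL is a named secondary outcome, and section 11 says EQ-5D is collected so that quality-adjusted life years can be calculated. Those need health states after progression as well as before it.

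**Working it through.** **Inputs (section 13.1).** Median PFS 8.9 months (placebo) and 12.4 months (sorafenib), exponential; hazard ratio (HR) 0.72; 12-month PFS on placebo 35% (range 30–40%) with a 12-point gain; 206 patients per arm; 36 months of accrual plus 12 of follow-up; two-sided 5%; 85% power; at least 340 events. Section 12.1 counts death from any cause as a PFS event.

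**Step 1: do these inputs reproduce the plan's own figure?**
- Freedman: (1.960 + 1.036)² × (1.72/0.28)² gives 339 events.
- Schoenfeld: 4 × (1.960 + 1.036)² / (ln 0.72)² gives 333 events.
- Expected events: the proportion with an event is 1 − [exp(−12λ) − exp(−48λ)]/(36λ), which is 0.868 and 0.780. With 206 per arm this gives about 339.5.

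These agree with the stated 340, so the PFS assumptions are a fair basis for the next steps.

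**Step 2: share with a PFS event before month 12.** λ = ln 2 / median; share = 1 − exp(−12λ).
- Placebo: λ = 0.0779; 1 − 0.393 = 60.7%
- Sorafenib: λ = 0.0559; 1 − 0.511 = 48.9%
- Pooled: 54.8%, about 226 of 412

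The stated 12-month rates give slightly higher shares:

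| 12-month PFS, placebo / sorafenib | Event, placebo | Event, sorafenib | Pooled |
|---|---|---|---|
| 30% / 42% | 70% | 58% | 64% |
| 35% / 47% | 65% | 53% | 59% |
| 40% / 52% | 60% | 48% | 54% |

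The gap between arms is 12 points throughout.

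**Step 3: share of the 12-month window without planned QoL.** Mean progression-free time within 12 months = (1 − exp(−12λ))/λ.
- Placebo: 7.80 months; 1 − 7.80/12 = 35%
- Sorafenib: 8.74 months; 1 − 8.74/12 = 27%

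**Step 4: allowing for deaths without progression.** In quality-adjusted survival, time after death counts as zero and is not missing, so steps 2 and 3 give upper bounds for that analysis. The protocol states no share of PFS events that are deaths first. As an assumption, let it run from 0 to 30%, equal in both arms:

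| Death-first share | Progressed by month 12, pooled (exponential medians) | Pooled (35% / 47%) |
|---|---|---|
| 0% | 55% | 59% |
| 10% | 49% | 53% |
| 20% | 44% | 47% |
| 30% | 38% | 41% |

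The pooled share falls below half once deaths first exceed about 9% (exponential) or 15% (35% / 47%) of events. Even at 30% the exponential figures are 42.5% on placebo and 34.2% on sorafenib, so the imbalance remains.

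**The case against.** Several points on the other side are sound.

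- **A reader might infer that the analyses have no data for over half of the patients.** They do not support that. Patients who progress lose only the part of the window after progression; at least 65% (placebo) and 73% (sorafenib) of the window lies within planned collection. On the exponential medians the sorafenib arm is itself just under half, and the pooled majority depends on how many PFS events are deaths.
- **A reader might infer that quality-adjusted survival would rest on imputed values.** Section 13.2 describes no imputation, and it does mention censored QoL in patients remaining alive, which can include patients alive after progression. What that wording leaves open is that this censoring is informative and differs by arm.
- **The AUC is called standardised and is of observed QoL.** It may be meant as a time-averaged score over whatever was observed. That reading is possible, but the result is then a progression-free average, not a measure over a complete 12 months.
- **Post-progression QoL would be hard to interpret.** Sections 7.2 and 12.5 unblind patients at progression, and section 3.2 lets placebo patients receive sorafenib. This is a real limit on the data, though a comparison by randomised group over 12 months still needs them.

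The QoL study is also by consent, so its denominator may be smaller than 412. That changes the counts but not the mismatch.

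**Conclusion.** The mismatch between the collection and analysis windows stands, and it lies in the protocol itself. On the protocol's medians, up to 61% of placebo and 49% of sorafenib patients end QoL collection before month 12 because of a PFS event, and up to about 35% and 27% of the window has no planned QoL. The figures rest on exponential PFS and the assumed treatment effect. For quality-adjusted survival they are upper bounds on the loss from the stopping rule; non-return and dropout would come on top. Earlier loss on placebo follows only if sorafenib works as assumed.

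The figures measure missing time. A reader might go further and put a size or direction on the resulting bias, but that depends on QoL after progression, on which the protocol gives no figures. The point concerns one secondary outcome and does not touch the PFS analysis. It should be settled while booklets can still be collected, because the loss cannot be repaired afterwards.

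**What to change.** Preferred: continue the QoL booklet to month 12 from randomisation regardless of progression, using the post-progression follow-up contacts, since the scheduled six-weekly visits themselves end at progression. Align sections 8.7, 11 and 12.6 and Appendix 12, and reconcile the flowchart's last column header with the six-weekly schedule in the text. State in section 13.2 that QoL after progression is collected after unblinding and possible crossover, and that the comparison is by randomised group.

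The cost is a few more questionnaires for patients already in follow-up, a modest burden on them, incomplete returns, and the interpretive limits just named.

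If this is not accepted, describe both the AUC and the quality-adjusted survival analysis as covering the progression-free period, and drop the claim to 12 months. That costs only wording, but gives up the 12-month comparison and leaves EQ-5D without the post-progression part needed for quality-adjusted life years.

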13.3 Planned subgroup analyses

Hazard ratios of the treatment effect (without significance testing) within identified prognostic subgroups, including stratification factors, will be estimated and presented graphically with tests of heterogeneity.

13.4 Planned Interim Analyses

Reports for the DMC will be produced by the trial statistician. A first report will be prepared based on the first 30 patients recruited into each treatment group or when the study has been open to recruitment for at least 12 months, whichever is the sooner. This aim of this initial report is to assess recruitment, compliance to treatment, toxicity (including reported serious adverse events) and 30-day mortality rates, specifically in relation to the combination of sorafenib with TACE.

Thereafter the DMC will meet annually, or more often if requested by the DMC, to monitor recruitment and toxicity (including reported serious adverse events) as well as assessment of primary and secondary outcome measures including response rates and survival. The DMC will be requested to consider the trial data accounting for other current worldwide evidence as well as review and make recommendations regarding the continuation of the study and the validation of the underlying assumptions for the sample size.

The trial may be stopped or amended by the Trial Steering Committee if proof beyond reasonable doubt emerges that one or other treatment is clearly indicated or contraindicated as considered by the DMC in light of the interim analyses. In terms of efficacy, the DMC would have to be in no doubt that there should be a change to clinical practice and would have to feel that it was unethical to continue to randomise. Regarding safety, the DMC would have to be in no doubt that safety was a major concern and would have to feel that it was unethical to continue to randomise. If any change to the trial is recommended, a substantial amendment will be submitted to MREC and MHRA prior to implementation.

13.5 Planned Final Analyses

Final analysis of the trial is planned when all alive patients have been followed up for a minimum of 12 months after their last blinded treatment visit.

13.6 Bayesian Analyses

A Bayesian analysis will be conducted alongside the frequentist analysis of the TACE-2 trial data to provide additional information regarding the treatment effect both at interim and final analyses. The Bayesian analysis will be purely exploratory and complementary to the frequentist analysis and in no way will influence the decision-making process of the TACE-2 trial.

Bayesian analysis has been recommended for use in clinical trials (Parmar et al, Lancet 2001; Berry, Nature Reviews 2006) and provides a probability distribution for the true treatment effect (known as the posterior distribution) by combining current trial data with prior information. The treatment effect is usually expressed in the form of a hazard ratio

(HR) and in this study a HR<0.72 has been deemed to be clinically relevant. The prior information takes the form of a probability distribution for the true treatment effect prior to the trial results being generated and this can be based on clinical opinion (elicited or represented by 'off-the-shelf' distributions) or can be evidence-based. Alternatively, the analysis can use a non-informative prior in which case the trial data would dominate the analysis. A Bayesian approach can enable the following research questions to be answered: i) "what is the probability that there is a true treatment effect (i.e. HR<1) and that it is clinically relevant (i.e. HR≤0.72)?", ii) "what is the predicted result for the trial based on current evidence?" and iii) "what are the chances of getting a statistically significant result if we continue?". The aim in this study is to run a Bayesian analysis alongside the frequentist analysis of the TACE-2 trial data to provide complementary additional information regarding the treatment effect both at interim and final analyses.

14 DATA HANDLING AND RECORD KEEPING

14.1 Data Collection and Case Report Form

The Investigator or designee, will record data as accurately and completely as possible on each patient, as soon as the requested information is available. The Investigator will be responsible for the timing, completeness and accuracy of the patient's Case Report Form (CRF). The Investigator will supply the TACE-2 Trials Office with any required background data from such records.

The Table below gives the CRF reporting timelines to the Trial office:

Case Report Form:	Time point	Timelines for completion & return to Trial office
Randomisation Form	Randomisation	Within 1 month of randomisation
Eligibility Checklist	Randomisation	Within 1 month of randomisation
On study form	Randomisation	2-5 weeks post randomisation
Pre-TACE Form	Up to 72h pre-TACE	Within 2 weeks after TACE
Embolisation Form	At embolisation	Within 2 weeks after TACE
1 Week Post-TACE Form	1 week post TACE	Within 3 weeks after TACE
Follow-up Form	Week 10 post rand and 6 weekly thereafter	Within 1 month of scheduled visit
Progression Notification Form	When applicable	ASAP but within 7 days of becoming aware of progression

Disease Assessment Form	Week 10 post rand and 12 weekly thereafter	Within 1 month of scheduled visit
End of Study Treatment Form	End of study treatment	Within 2 weeks of event
Post Progression Follow-up Form	Routine follow-up visits post progression	Within 1 month of visit
Serious Adverse Event Form	When applicable	Within 24 hours of becoming aware of the event
Study Deviation form	When applicable	Within 2 weeks of event
Withdrawal Form	When applicable	Within 2 weeks of event
Death form	When applicable	Within 2 weeks of event

The database for the TACE-2 trial is a web based system that will allow electronic data entry at site via the website: https://www.cancertrials.bham.ac.uk/TACE2. Hospital staff involved in the trial will be provided with unique log in details to access the database and data validation will be provided through the database system. All data entered will be transcribed from the source data (see section 3.7).

The CRF may be amended during the course of the trial; this will not constitute a protocol amendment. Revised CRF will be circulated to participating sites with immediate effect; sites should ensure they are using the most recent version of the CRF.

Data reported on the CRF should be consistent with the source data (see section 3.8) or the discrepancies should be explained. If the information is not known, this must be clearly indicated e.g. by entering Not Known (NK) on the form.

The TACE-2 trial team at the University of Birmingham will be responsible for ensuring completeness of trial data. All missing or ambiguous data will be queried by email, telephone or writing to centres.

To maximise completeness of data, the site will be requested to call patients who have missed scheduled appointments for specific assessments and reschedule another appointment. For patients who have consented to take part in the quality of life study, the site will call patients who have not returned questionnaires to chase the questionnaire.

14.2 Archiving

It is the responsibility of the Principal Investigator to ensure all essential trial documentation and source records (e.g. signed Informed Consent Forms, Investigator Site Files, Pharmacy Files, patients' hospital notes, copies of CRFs etc) at their site are

securely retained for at least 15 years after the end of the trial. Participating sites will be sent a letter specifying the permissible disposal date.

